### **5.3.6 IOL Observations**

IOL observations will be summarized by lens model using descriptive statistics, including frequency (N) and percent of eyes, separately for first and second implanted eyes, at each scheduled and unscheduled visit where the data were collected. "Other" IOL observations will be summarized and sorted by subject identification (investigator number, subject number), treatment, and by visit, separately for first and second implanted eyes.

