8.4.2 Safety Endpoints

Safety endpoints are listed below.

- Rates of ocular adverse events, including SSIs related to the optical properties for either eye
- Adverse events
- Device deficiencies
- IOL observations
- Subjective PCO
- Posterior Capsulotomies

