1. Record changes in medical/ocular history and ocular and non-ocular concomitant medications.
2. Administer patient satisfaction question. For question, refer to Appendix Section 18.1.
3. [REDACTED]
4. [REDACTED]
5. [REDACTED]
6. Assess binocular uncorrected distance visual acuity.
[Both Eyes, Binocular]
7. [REDACTED]
8. Assess binocular uncorrected near (40 cm) visual acuity.
[Both Eyes, Binocular]
9. [REDACTED]

10. Assess binocular uncorrected intermediate (60 cm) visual acuity.
[Both Eyes, Binocular]
11. Perform defocus testing.
[Both Eyes, Binocular]
12. Perform mesopic without glare contrast sensitivity testing.
[Both Eyes, Binocular]
13. Perform mesopic with glare contrast sensitivity testing.
[Both Eyes, Binocular]
14. Perform photopic without glare contrast sensitivity testing.
[Both Eyes, Binocular]
15. Perform photopic with glare contrast sensitivity testing.
[Both Eyes, Binocular]
16. Perform slit lamp examination of the anterior segment. Include documentation of IOL observations, if any.
[Both Eyes, Bilateral]
17. Observe any IOL position changes (ie, tilt and decentration) occurring since the previous visit.
[Both Eyes, Bilateral]
18. Assess subjective PCO, and record information for any posterior capsulotomy that has occurred since surgery, if applicable.
[Both Eyes, Bilateral]
19. Perform dilated fundus exam noting any issues with fundus visualization due to the lens optic.
[Both Eyes, Bilateral]
20. Perform tonometry to measure the IOP.
[Both Eyes, Bilateral]

21. Record any AEs including SSIs.

Note: Serious adverse events (SAEs) including SSIs must be entered into EDC within 24 hours of the Investigator's knowledge. Refer to Section 13 for further detail.

22. Record any device deficiencies. Refer to Section 13 for further detail.

12.2 **Unscheduled Visits**

An unscheduled visit (UNSV) is defined as follows:

- Ocular examination that is not standard of care and not required by the protocol;
- Examination conducted by the study staff;
- New findings, or a change to a previous finding was discovered; and
- Not site standard of care/routine.

An UNSV may or may not result in the capture of an adverse event. Likewise an adverse event may be captured without the report of an UNSV (eg, AE identified subsequent to study eye examination by non-study personnel).

The assessments captured at the UNSV are dictated by the Investigator per his/her medical judgment. The following assessments are recommended.

- Concomitant medications

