15.7 Safety Analysis

Adverse Events

All information obtained on AEs will be displayed by treatment and subject.

The number and percentage of all ocular adverse events, including secondary surgical interventions (SSIs) for either eye, will be tabulated by preferred term with a breakdown by treatment and implanted eye. An eye with multiple ocular AEs of the same preferred term is only counted once toward the total of this preferred term.

The number and percentage of all adverse events will also be tabulated with a breakdown by treatment.

Device Deficiencies

The number and percentage of all device deficiencies will be tabulated with a breakdown by treatment and implanted eye. A listing of all device deficiencies will also be provided.

IOL Observations

The number and percentage of all IOL observations will be tabulated with a breakdown by treatment and implanted eye.

Subjective Posterior Capsule Opacification

The number and percentage of eyes within each category of subjective posterior capsule opacification will be tabulated with a breakdown by treatment and implanted eye.

Posterior Capsulotomy

The number and percentage of eyes with posterior capsulotomy will be tabulated with a breakdown by treatment and implanted eye.

Other Safety Assessments

All other safety assessments (including intraocular pressure, slit lamp examination, IOL position change, fundus visualization, dilated fundus examination and surgical problems) will be summarized. Number and percentage will be presented for categorical variables and descriptive statistics including mean, standard deviation, minimum and maximum will be presented for continuous variables.

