### **5.3.1 Adverse Events**

All information obtained on AEs will be displayed by treatment and subject.

The number and percentage of all ocular adverse events, including secondary surgical interventions (SSIs) for either eye, will be tabulated by preferred term with a breakdown by treatment, separately for first and second eyes. An eye with multiple ocular AEs of the same preferred term is only counted once toward the total of this preferred term.

The number and percentage of all adverse events will also be tabulated with a breakdown by treatment, separately for first and second implanted eyes.

Adverse events will be summarized in the following tables:

1. All Adverse Events (Serious and Non-Serious Combined)
  - a. Ocular
  - b. Non-Ocular
2. All Adverse Device Effects
  - a. Ocular
  - b. Non-Ocular
3. All Serious Adverse Events (including Serious Adverse Device Effects)
  - a. Ocular
  - b. Non-Ocular
4. Subject Listings
  - a. Non-Serious Ocular
  - b. Non-Serious Non-Ocular
  - c. Serious Ocular
  - d. Serious Non-Ocular

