### **5.3.5 Slit Lamp Examination**

For each slit-lamp parameter, number and percentages of eyes that experience abnormality at any post-operative visit will be presented, separately for first and second implanted eyes.

A listing will be provided which presents all eyes with an abnormality in any slit-lamp parameter at any post-operative visit. The listing will include all slit-lamp data from all visits with the following variables: treatment, investigator, subject, age, sex, race, ethnicity, visit, eye, parameter, baseline value, and value at the visit.

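### SAP 5.3.6 summarises IOL observations, a protocol safety endpoint, only by visit, so no planned row shows how many eyes were ever affected, and no denominator is stated

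*SAP*

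**What the plan says.** Protocol 8.4.2 includes "IOL observations" among the safety endpoints. For their analysis, Protocol 15.7 states: "The number and percentage of all IOL observations will be tabulated with a breakdown by treatment and implanted eye". That sentence has no split by visit. It also names no denominator and does not say that an eye counts once.

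SAP 5.3.6 summarises the observations by lens model, "including frequency (N) and percent of eyes, separately for first and second implanted eyes", and does so "at each scheduled and unscheduled visit where the data were collected". It contains no summary over the whole of follow-up, no denominator, and no rule for an eye that attends several unscheduled visits. Subject-level output is planned only for observations classed as Other.

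Neighbouring SAP sections do summarise over follow-up:

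- 5.3.5 (slit lamp): "number and percentages of eyes that experience abnormality at any post-operative visit will be presented". Section 5.3.11 (dilated fundus) takes the same approach.
- 5.3.4 (IOP): the any-visit table places each eye once, in its category of maximum change.
- 5.3.1 (ocular adverse events): "An eye with multiple ocular AEs of the same preferred term is only counted once toward the total of this preferred term".

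Protocol 12.2 defines an unscheduled visit by several joint conditions, one of which is: "New findings, or a change to a previous finding was discovered". The assessments made there are left to the investigator's judgement.

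**The concern.** For a lens-specific safety endpoint, the first question is how many eyes with each lens ever showed a given observation. By-visit rows do not answer it. The same eye may appear in several rows, or different eyes may appear in different rows, and the table looks the same in both cases. An observation made only at an unscheduled visit appears in no scheduled row. The unscheduled row cannot simply be added to the others, because its eyes overlap with theirs.

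The unscheduled row raises a second question. Eyes seen at such visits are a selected group, and an eye may attend more than once. A percentage based on that group would not describe the implanted eyes. What is at stake is whether the two lenses can be compared on this endpoint from the planned tables.

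**Working it through.** The documents give no rate for IOL observations, so there is no plan figure to reproduce. All rates and affected-eye counts below are assumptions chosen to show the range.

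**Inputs**

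- Eyes per arm: about 160 subjects, 1:1 (SAP 7), so 160 / 2 = 80 first eyes and 80 second eyes per arm.
- Scheduled postoperative slit-lamp visits per eye: four (Protocol 12.1.3 to 12.1.6). First eyes are seen at Visits 1, 2, 3A and 4A, and second eyes at 1A, 2A, 3A and 4A.
- Simplification: all 80 eyes are examined at every scheduled visit.

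**Step 1: what the scheduled rows say about eyes ever affected**

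Let p1 to p4 be the four visit rates. The share ever affected at a scheduled visit lies between max(p1, …, p4), when the same eyes are affected throughout, and min(1, p1 + p2 + p3 + p4), when different eyes are affected each time. If the visits were independent with a common rate p, the share would be 1 − (1 − p)^4.

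| Assumed rate at each visit | Affected eyes per visit, of 80 | Lowest share | Independent visits | Highest share |
|---|---|---|---|---|
| 2.5% | 2 | 2.5% | 9.6% | 10% |
| 5% | 4 | 5% | 18.5% | 20% |
| 10% | 8 | 10% | 34.4% | 40% |

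In the middle row, the same four eyes at each visit give 4/80 = 5%, and sixteen different eyes give 16/80 = 20%. Two arms could therefore have identical scheduled rows and differ by a factor of 20 / 5 = 4 in eyes ever affected. Eyes affected only at an unscheduled visit would come on top of these figures.

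**Step 2: the unscheduled row under two denominators**

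Assume 3 eyes with an observation at an unscheduled visit.

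| Eyes examined at unscheduled visits | Percent of eyes examined | Percent of all 80 eyes |
|---|---|---|
| 3 | 100% | 3.75% |
| 5 | 60% | 3.75% |
| 8 | 37.5% | 3.75% |
| 12 | 25% | 3.75% |

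The SAP wording on data collection suggests the first denominator but does not state it. With all Safety Set eyes as the base, the second applies and the selection has no effect on the percentage.

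**Step 3: can another planned output supply the missing row?**

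- Protocol 15.7 has no visit split, but it speaks of observations rather than eyes, and SAP 5.3.6 does not repeat it as an overall table.
- IOL observations are documented during the slit-lamp examination. SAP 5.3.5, however, works by slit-lamp parameter and lists only eyes with an abnormality. It does not say whether an IOL observation counts as a parameter, and the SAP gives these observations a section of their own.
- The sorted summary in 5.3.6 covers only the Other category.

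None of these clearly yields the number and percentage of eyes ever affected.

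**The case against.** The strongest defence has four parts.

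- **Counts are shown.** A reader might infer that the table hides small bases behind bare percentages. It does not: SAP 5.3.6 gives N with each percentage, so a handful of eyes in the unscheduled row would be visible. This stands.
- **The unscheduled percentage need not be distorted.** A reader might infer that the definition of an unscheduled visit inflates it by construction. The documents do not support that. SAP 5.3 makes the Safety Set the default analysis set, and the phrase about data collection may only say which visits are tabulated. The finding that defines the visit may also be of any kind, so the definition selects eyes without forcing a high rate of IOL observations. What remains is an unstated denominator.
- **By-visit summaries are legitimate.** They show onset and persistence, and for a lasting observation the Visit 4A row approximates the cumulative share. This is fair, and it is why the scheduled rows should stay. It does not help with transient observations or those seen only at unscheduled visits.
- **Nothing formal depends on it.** SAP 5.2 has no safety hypotheses, and secondary surgical interventions and device deficiencies are reported elsewhere. This limits the weight of the point but does not supply the missing row.

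A reader might also infer that the SAP breaks an explicit protocol promise of a per-eye count, or that a real difference between the lens materials would be missed. Protocol 15.7 does not specify counting each eye once, and no document figure shows how observations would spread over visits or arms.

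**Conclusion.** The point holds as a limited gap in a descriptive table. As written, SAP 5.3.6 yields no percentage of eyes ever affected for a named safety endpoint. Its layout differs from Protocol 15.7 and from the SAP's own practice in 5.3.4, 5.3.5 and 5.3.11. That part follows from the text alone.

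The sizes are illustrations. The 5% to 20% range assumes a 5% rate at each of four visits with full attendance. The contrast of 60% with 3.75% assumes 3 affected eyes among 5 examined, and arises only if the base is eyes examined at unscheduled visits. The share ever affected could be derived later from data already collected. No primary, secondary or success criterion is affected. The change is worth making because it is cheap and makes the endpoint directly readable.

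**What to change.** Add to SAP 5.3.6, as the main summary, by lens model and separately for first and second eyes:

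> Number and percentage of eyes with each IOL observation at any postoperative visit, scheduled or unscheduled. Each eye is counted once per observation. The denominator is Safety Set eyes with at least one postoperative slit-lamp examination.

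Keep the scheduled-visit rows as support and state their denominator. Report findings from unscheduled visits as counts, or in an added listing, without a percentage. SAP 5.3.6 currently has no general listing of IOL observations, so that option means creating one.

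The cost is one extra table block and, if chosen, one listing. No additional data collection is needed.

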### **5.3.7 IOL Position Change**

Descriptive statistics (number and percentages) on eyes with a change from baseline in IOL position category (Tilted, Decentered) will be presented, separately for first and second implanted eyes. In addition, a listing of eyes with IOL position change will be provided. The listing will include the following variables: investigator, subject, age, sex, race, ethnicity, treatment, visit, eye and amount of tilting or decentration.

### **5.3.8 Subjective Posterior Capsule Opacification**

The number and percentage of eyes within each category of subjective posterior capsule opacification will be tabulated with a breakdown by treatment, separately for first and second implanted eyes.

### **5.3.9 Posterior Capsulotomy**

The number and percentage of eyes with posterior capsulotomy will be tabulated with a breakdown by treatment, separately for first and second implanted eyes.

### **5.3.10 Fundus Visualization**

The fundus visualization will be performed to document whether the lens causes any difficulty in viewing and/or examining the retina or posterior segment, or affects the

surgeon's ability to administer vitreal/retinal treatments, as compared to experience with monofocal IOLs.

Descriptive statistics (number and percentages) on eyes with difficulty in viewing and/or examining the retina or posterior segment will be presented, separately for first and second implanted eyes. In addition, a listing of eyes with fundus visualization difficulty will be provided. The listing will include the following variables: investigator, subject, age, sex, race, ethnicity, treatment, visit, eye and type of difficulty.

### **5.3.11 Dilated Fundus Examination**

For each dilated fundus parameter, number and percentages of eyes that experience abnormality at any post-operative visit will be presented, separately for first and second implanted eyes.

A listing will be provided which presents all eyes with abnormality in any fundus parameter at any post-operative visit. The listing will include the following variables: investigator, subject, age, sex, race, ethnicity, treatment, visit, eye, baseline value and value at the visit.

## **5.4 Interim Analysis for Safety**

An interim analysis will be performed when all subjects complete Visit 3A (20-40 days post 2nd eye implantation) in order to support the study publication plan of the test articles for adverse events.

Adverse events analyses as described in Section 5.3.1 will be generated for the interim analysis results.

## **6 Analysis Strategy for Other Endpoints**

Not applicable.

## **7 Sample Size and Power Calculations**

The multiplicity adjustment strategy is outlined in Figure .4-1. Sample size estimations are based on the minimum sample size needed to achieve 90% power for all hypothesis tests. A type I error rate of 2.5%, one-sided, is used for calculations to account for simultaneous testing in Gate 2 (see Figure .4-1).

Assuming a dropout rate of 5%, approximately 160 subjects will be bilaterally implanted in 1:1 allocation ratio (test: control) to achieve at least 152 subjects who complete the study. With 152 subjects (76 per group) there is 98% probability that an upper one-sided 97.5%

confidence limit on the difference (test-control) in visual acuity will be less than 0.1 logMAR, assuming the mean difference of 0.0 logMAR and a common standard deviation of 0.16 logMAR, the maximum observed for binocular uncorrected distance, intermediate and near visual acuity in a previous Alcon study (C-06-40, ReSTOR +3.0 D IOL).

[figure not shown]
Also, with 76 subjects per group, there is more than 90% power to detect a difference of 0.09 logMAR (4.5 letters) between means in a two sample t-test conducted at a 2.5% chance of a Type I error and assuming a standard deviation of 0.16 logMAR for binocular uncorrected distance, intermediate and near visual acuity.

## **8 References**

Not applicable.

## **9 Revision History**

This is the original (Version 1.0) Statistical Analysis Plan for this study. This version of the Statistical Analysis Plan is based on Version 2.0 of the study protocol.

[figure not shown]
[figure not shown]
[figure not shown]
[figure not shown]
[figure not shown]
[figure not shown]
[figure not shown]
11 Appendix

Table .11-1 Schedule of Visits

Activity	Bin-ocular	1 st Eye			2 nd Eye			Binocular		Mon-ocular
	Visit 0	Visit 00	Visit 1	Visit 2	Visit 00A	Visit 1A	Visit 2A	Visit 3A	Visit 4A 	UNSV 
	Day -60 to 0 Preoperative	Day 0 1 st Eye Implantation	1-2 Day Post 1 st Eye Implantation	7-14 Days Post 1 st Eye Implantation	2-21 Days Post Visit 00 2 nd Eye Implantation	1-2 Day Post 2 nd Eye Implantation	7-14 Days Post 2 nd Eye Implantation	20-40 Days Post 2 nd Eye Implantation	120-180 Days Post 2 nd Eye Implantation	N/A
Informed Consent	X									
Demographics	X									
Medical History	X									
Concomitant Medication	X	X	X	X	X	X	X	X	X	X
Urine Pregnancy Test 	X									
Inclusion/Exclusion	X	X			X					
Randomization 		X								
Surgery/Treatment		X			X					
Report Implanted Lens Model		X			X					

Activity	Binocular	1 st Eye			2 nd Eye			Binocular		UNSV 
	Visit 0	Visit 00	Visit 1	Visit 2	Visit 00A	Visit 1A	Visit 2A	Visit 3A	Visit 4A 	
Surgical Report (Including: lens power, implant success, target refractive error  and success of implantation)		X				X				
Problems During Surgery		X				X				
Other Surgical Procedures		X				X				
Patient Satisfaction									X	
Distance VA (4 m)										
• Monocular Uncorrected										X

	Bin-ocular	1 st Eye			2 nd Eye			Binocular		Mon-ocular
	Visit 0	Visit 00	Visit 1	Visit 2	Visit 00A	Visit 1A	Visit 2A	Visit 3A	Visit 4A 	UNSV 
Acuity										
Contrast Sensitivity (Binocular)										

 
Mesopic without Glare
 
								X	X	

 
Mesopic with Glare
 
								X	X	

 
Photopic without Glare
 
								X	X	

 
Photopic with Glare
 
								X	X	
Slit-Lamp Examination (Including IOL Observations)	X		X	X		X	X	X	X	X
IOL Position Change			X	X		X	X	X	X	X
Subjective PCO			X	X		X	X	X	X	X
Posterior Capsulotomy (Repeat if performed)			X	X		X	X	X	X	X
Fundus Visualization								X	X	

Printed By:

Print Date:

Activity	Bin-ocular	1 st Eye			2 nd Eye			Binocular		Mon-ocular
	Visit 0	Visit 00	Visit 1	Visit 2	Visit 00A	Visit 1A	Visit 2A	Visit 3A	Visit 4A 	UNSV 
	Day -60 to 0 Preoperative	Day 0 1 st Eye Implantation	1-2 Day Post 1 st Eye Implantation	7-14 Days Post 1 st Eye Implantation	2-21 Days Post Visit 00 2 nd Eye Implantation	1-2 Day Post 2 nd Eye Implantation	7-14 Days Post 2 nd Eye Implantation	20-40 Days Post 2 nd Eye Implantation	120-180 Days Post 2 nd Eye Implantation	N/A
Dilated Fundus Examination	X							X	X	X
IOP	X		X	X		X	X	X	X	X
Adverse Events (Including SSI)	X	X	X	X	X	X	X	X	X	X
Device Deficiencies		X	X	X	X	X	X	X	X	X

 If a subject exits early, the Visit 4A procedures should be performed at the last available visit, if at all possible.

 UNSV assessments listed are recommended. Only complete assessments required per the PI medical judgment.

 Women of child-bearing potential only

 Within 10 business days of treatment (Visit 00).

 Data is reported in EDC at the surgical visit, but may be collected at a previous visit.

Date/Time (mm/dd/yyyy GMT):	Signed by:	Justification:
07/11/2016 14:38:01	██████████ ██████████	██████████
07/12/2016 13:26:33	██████████ ██████████	██████████
07/12/2016 18:52:23	██████████ ██████████	██████████
07/12/2016 20:51:37	██████████ ██████████	██
